Exclusion criteria: Lifetime diagnosis of a psychotic disorder, not induced by drug use; current prescribed treatment of opioids or benzodiazepines, which may affect new learning; involvement in a legal case that may lead to incarceration during study period; residential plans that would interfere with participation; medical illness that may significantly compromise cognition (e.g. Parkinson's, Alzheimer's, Huntington's Chorea, Moderate or greater TBI); an uncorrected sensory impairment (hearing or sight) that would seriously interfere with cognitive training; pre-morbid IQ estimate below 70; unstable housing or lack of commitment to staying within a geographic area that would make follow-up possible); unwillingness to provide contact information of someone who can help us contact the participant in the event that we are unable to maintain contact directly. They must be competent to give written informed consent and HIPAA authorization.

**Measures:** Primary outcome measures are Heavy Drinking Days and Days of Use for the 90 days of active intervention as measured by Time-Line Follow-back (TLFB) Alcohol Use Assessments. This assessment asks for days of use and how many drinks and what types of drinks were consumed at each occasion during the preceding week. Other drug use is also recorded. TFLB assessment is done weekly along with an alcohol urine toxicology test and a Breathalyzer test. If more than one week has passed since the last TFLB assessment, the TLFB procedure is used to review the entire lapsed period. For example, if it has been 14 days since the last TLFB, then going backwards, the interviewer would ask about alcohol use for those 14 days. Breathalyzer testing and an alcohol urine toxicology test is always performed first, followed by the TFLB. This sequence encourages disclosure even though Breathalyzer results only reflect alcohol use during the past day. The alcohol urine toxicology test reflects a window of up to 80 hours of prior use. A positive Breathalyzer test and an alcohol urine toxicology test is regarded as definitive evidence of alcohol use and has precedence over self-report when the person denies use. However a negative Breathalyzer test or a negative alcohol urine

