toxicology test is not regarded as evidence of abstinence when the person states that he/she used alcohol. Secondary outcomes include Heavy Drinking Days and Days of Use for the 30 days preceding 6 month follow-up using Breathalyzer and the Time-Line Follow-back procedure.. Changes in Alcohol Craving from baseline at 3 and 6 month follow-up will be examined. Neurocognitive outcomes at 7 weeks and at 3 month and 6 month follow-ups are also secondary outcomes. Measures are presented in the following chart by category. They include AUD related assessments and cognitive assessments by domain. These domains include attention, working memory, learning and memory, executive function, and processing speed. We also include measures of risk taking and impulsivity because they are strongly associated with AUD and may be inhibited by improved executive functions. A treatment utilization form is included as a weekly measure of treatments received beyond study procedures. Given space limitations, descriptions are not provided, but references are included. From our experience in the R21, which used very similar assessments, Baseline is estimated to be 3-4 hours and follow-up evaluations are 2-3 hours. Inter-rater agreements were in the good to excellent range in prior studies and in the R21, and agreement drift is checked through consensus meetings.

Instrument	Source	Blinded	Baseline	Weekly	7wks	13wks	26wks
Inclusion/Exclusion	Chart + Interview						
Demographics & M.I.N.I 	Interview		X				
AUD Related Assessments							
EtG Urine Tox Screen			X	X		X	X
Alcohol Breathalyzer		X	X	X		X	X
Time-Line Follow-back Alcohol Use Calendar 	Interview	X	X	X		X	X
Addiction Severity Index modified 	Interview	X	X			X	X
Drug Urine Tox Screen			X			X	X
Penn Alcohol Craving Scale 	Self		X	X		X	X
Premorbid-IQ Estimate							
Wechsler Test of Adult Reading (WTAR) 	Perform	X	X				
Attention							
Integrated Visual & Auditory Continuous Performance Test-2 	Perform	X	X		X	X	X
Trails A & B 	Perform	X	X		X	X	X
Working Memory							
Digit Span 	Perform	X	X		X	X	X
Spatial Span 		X	X		X	X	X
Learning and Memory							
Hopkins Verbal Learning Test (multiple forms) 	Perform	X	X		X	X	X
Logical Memory I + II 	Perform	X	X		X	X	X
Brief Visual Motor Test 	Perform	X	X		X	X	X

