## **Data Management, Sample Size Calculation, and Analysis Plan**

Data management will follow procedures established in previous studies. Our research team will use Teleforms® software to create, clean, and enter quantitative data. Forms are created with barcodes that are scanned using Teleforms' object character recognition software. Data is extracted and automatically inputted to an SPSS database. Filters flag data that needs to be re-checked by a person such as unclear characters, out-of-range variables and logical inconsistencies. The research assistant will scan files monthly so that errors can be readily corrected and consequential differences between treatment types (e.g., different levels of attrition) can be monitored closely. SPSS (vers. 21) will be used as the primary analysis software. Baseline characteristics will be tested for any significant differences between randomized conditions using parametric and non-parametric procedures as required by the nature of the data. Data reduction is a major issue in a relatively small N, large-number-of-variables study. We have chosen a primary outcome measure (Heavy Drinking Days and Days of Use in the first 90 days) to reduce Type I error. Heavy Drinking Days and Days of Use will be determined by Time-Line Follow-back calendar and Breathalyzer results. If a participant cannot provide more exact information about days of use for that week, then we will assume continuous use.

Neuropsychological data will be indexed into established domain scores (attention, working memory, memory and learning, executive function, processing speed) and a composite index score. The design is intent-to-treat. Distributions of continuous data will be tested for normality and transformed when necessary. Randomized conditions will be tested for potential differences on baseline values. We believe that our stratified randomization will make it unlikely that significant differences will be found; however, any significant differences will be used as covariates in between-group comparisons.

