Analysis Plan: We will use a Poisson regression model accounting for over-dispersion to compare the CRT+IDC arm to the Game-Play Placebo+IDC arm on the primary outcomes: Days of Use and Days of Heavy Drinking at 90 days (Ho1). We will use the same model to compare the CRT+IDC arm to the Game-Play Placebo+IDC for the 6 month time point, a secondary endpoint (Ho2). We will conduct sensitivity analysis using a negative binomial model and assess any differences in the results compared to the Poisson model with over-dispersion. To evaluate neurocognitive functioning (global index; index of working memory; index of executive function, etc..), we will use generalized estimating equations and/or linear mixed models (if the data appear normally distributed) to account for the correlation between time points (baseline, 3 months, 6 months) for a given individual. We will test for a significant treatment arm by time interaction to determine whether the combination of CRT+IDC is more effective than Game-Play Placebo+IDC in improving neurocognitive outcomes (Ho3, Ho4). We use contrast statements to explore the individual time point effects. In all models, we will adjust for neurocognitive functioning (the stratification variable). We will use the Benjamini-Hochberg procedure to control the false discovery rate for all secondary outcomes keeping the overall level of significance at 0.05. However, given the limited sample size in this study, we do not expect to reach statistical significance unless there are large effects, especially for the secondary outcomes, and thus plan to use these results as hypothesis generating for a larger confirmatory study.

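### Covariates beyond the stratum are picked by baseline significance tests, so the primary models are not fixed in advance and baseline drinking enters only by chance; any precision lost depends on an unreported correlation

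*Combined protocol and SAP*

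**What the plan says.** All of this is in the combined protocol and SAP. The section on data management, sample size and analysis announces baseline testing twice: "Baseline characteristics will be tested for any significant differences between randomized conditions" and, a paragraph later, "Randomized conditions will be tested for potential differences on baseline values". It expects stratified randomisation to make significant differences unlikely, and adds that "any significant differences will be used as covariates in between-group comparisons". It gives neither a list of variables to be tested nor a threshold.

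The Analysis Plan paragraph compares days of use and heavy drinking days at 90 days by Poisson regression with over-dispersion. One covariate is fixed: "In all models, we will adjust for neurocognitive functioning (the stratification variable". For the secondary drinking endpoint it says: "We will use the same model to compare the CRT+IDC arm to the Game-Play Placebo+IDC for the 6 month time point". Baseline is a time point only in the neurocognitive models.

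The Measures table in section 6 marks the "Time-Line Follow-back Alcohol Use Calendar" at baseline, so baseline drinking is collected. Its baseline look-back is not stated. The Measures text covers drinks "consumed at each occasion during the preceding week", with an extension when a weekly visit has lapsed.

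**The concern.** In a randomised trial a significant baseline difference is a chance event. Its p-value does not show whether the variable predicts the outcome, and prediction is what makes a covariate useful. The rule can leave out a strong predictor that happens to be balanced and bring in an irrelevant variable that is not. Stratifying on cognition does not directly protect against an imbalance in drinking.

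Two things are at stake. First, the primary model is not fixed before the data are seen. Second, if baseline drinking predicts drinking on trial, precision is lost in a trial with about 40 analysed per arm. The plan expects significance only for large effects, especially on secondary outcomes, and says it will "plan to use these results as hypothesis generating for a larger confirmatory study". A covariate set chosen by chance is hard to carry into that larger study.

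**Working it through.** **1. The plan's own figures.** Inputs from the Sample size paragraph: 80 analysed; control means 4 (days of use) and 3 (heavy drinking days); over-dispersion φ = 2 and 4; reductions of 37% and 55% (rate ratios RR = 0.63 and 0.45); 5% error per outcome, taken as two-sided. The Poisson-regression formula is N = φ(z_a√V0 + z_b√V1)² / (μ·ln²RR), with V0 = 4 and V1 = 2 + 2/RR.
- Days of use: √(80 × 4 × 0.2135 / 2) = 5.844; (5.844 − 3.92) / √5.175 = 0.846; power 80.1%.
- Heavy drinking days: √(80 × 3 × 0.6376 / 4) = 6.185; (6.185 − 3.92) / √6.444 = 0.892; power 81.4%.

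Both figures reproduce, and neither uses a covariate.

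**2. How often the rule brings in baseline drinking.** At an assumed 0.05 threshold the chance is 5% per variable. For at least one of the two baseline counts it lies between 5% and 1 − 0.95² = 9.75%. In simulation, baseline drinking was selected in 4.5 to 5.6% of trials. With 14 independent tests (illustrative), at least one variable enters with probability 1 − 0.95¹⁴ = 51%.

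**3. Power.** Simulation with 40 per arm, two equal strata balanced by arm, the plan's means, φ and rate ratios, and 6,000 trials per cell (Monte Carlo error about √(0.77 × 0.23 / 6000) = 0.5 points). The baseline count is an assumption: binomial over 90 days less 0 to 30 sober days, with person-level drinking probability logistic in a latent trait. r is the realised correlation of that count with the 90-day outcome. The rule column tests baseline drinking alone.

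| Outcome | r | Stratum only | Rule | Count, HC3 | Change, count vs stratum only |
|---|---|---|---|---|---|
| Days of use | 0 | 76.5% | 76.3% | 74.4% | −2.1 |
| | 0.13 | 75.6% | 75.4% | 74.7% | −0.9 |
| | 0.27 | 76.8% | 76.7% | 77.7% | +0.9 |
| | 0.36 | 76.8% | 77.5% | 80.2% | +3.4 |
| | 0.44 | 78.0% | 78.5% | 83.5% | +5.5 |
| Heavy drinking days | 0 | 81.3% | 81.2% | 80.3% | −1.0 |
| | 0.14 | 82.1% | 82.1% | 81.9% | −0.2 |
| | 0.28 | 81.8% | 82.0% | 83.0% | +1.2 |
| | 0.37 | 83.1% | 83.5% | 85.9% | +2.8 |
| | 0.46 | 83.1% | 83.8% | 88.1% | +5.0 |

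One point is worth about one participant per arm: (1.96 + 0.74) / 80 × 0.303 = 0.010 per participant.

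**4. Number of variables tested.** Against stratum-only, the rule stays within 1 point for 1 or 5 variables, loses 0 to 2 points for 10, and loses 2 to 3 points for 22 that do not predict drinking. If 5 of the 22 do predict it, the loss is 0 to 2 points. The plan does not say how many will be tested.

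**5. Type I error and choice of standard error.** Under the null: rule 4.6 to 5.9%; count with HC3 4.2 to 5.2%; count with model-based errors 4.7 to 5.9% for days of use but 5.2 to 7.5% for heavy drinking days. For days of use, a further run of 4,000 trials per cell gave, for stratum-only, count model-based and count HC3: 77.4%, 76.8% and 75.7% at r about 0; 76.0%, 82.5% and 80.4% at r about 0.40. So HC3 costs about 1 to 2 points there and corrects nothing.

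**6. Six months.** Assumed 36 per arm (90 × 0.9 × 0.9 = 72.9), means scaled to 30 days, latent correlation 0.3/0.4/0.5. Count with HC3 against stratum-only: days of use 39.9/40.4/40.4% against 40.9/41.7/40.1%, or −1.0/−1.3/+0.3 points; heavy drinking days 55.1/55.1/57.9% against 55.1/54.6/55.5%, or 0/+0.5/+2.4 points.

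**7. Look-back.** In the same model a 7-day baseline count is zero for 81 to 82% of participants, has r of at most 0.09, and gives power 1 to 2 points below stratum-only.

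**The case against.** The best defence is that little is harmed. With few variables tested, the rule performs like stratum-only adjustment. The gain from the alternative rests on a correlation that the documents do not report, and weak prediction is plausible: participants enter newly abstinent, and the mixed-substance pilot's training arm averaged 97% abstinent days. This stands, and it limits the size of the point. It does not rescue the rule, which leaves the model open whatever r is.

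It can also be argued that the rule covers only the cognitive outcomes, because its sentence closes a paragraph that opens on neuropsychological data. But its wording refers to between-group comparisons in general, and baseline testing is also announced in the preceding paragraph, which deals with the drinking outcome. If the narrow reading is right, baseline drinking is simply never adjusted for, and the remedy for the primary models is the same.

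A reader might infer that testing baselines inflates type I error, or that the sample size is wrong. Neither follows: simulated error under the rule is 4.6 to 5.9%, and the stated reductions reproduce without covariates. A reader might also infer that robust errors and baseline adjustment belong in every drinking model. Steps 5 and 6 do not support that for days of use or for the 6-month models.

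**Conclusion.** The concern holds as one of pre-specification and efficiency. The covariate rule leaves the primary models undetermined and, read generally, admits baseline drinking only on a chance imbalance, about 5% of the time at an assumed 0.05 threshold. That part does not depend on r.

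The precision part is conditional. With HC3 errors, the pre-specified count moves power by about −1 to −2 points at r = 0, breaks even near r = 0.15 to 0.25, and gains about 3 to 6 points at r = 0.36 to 0.46. It would be too strong to say that the plan loses power for certain, since the documents give no r. The figures also rest on an assumed 90-day baseline count. Narrower or wider spreads of baseline drinking gave gains of 0 to 6 points at r of about 0.24 to 0.45.

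**What to change.** Replace the covariate rule with wording such as: *Baseline characteristics are summarised by arm without significance tests, and no covariate is added because of an observed difference. The primary 90-day models adjust for the randomisation stratum and for the baseline Time-Line Follow-back counterpart of the outcome, over the 90 days before consent. The heavy-drinking-days model uses HC3 robust standard errors; the days-of-use model uses model-based over-dispersed errors.*

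The 90 days are an example. What matters is one fixed look-back that reaches before the current abstinence. The Design paragraph puts consent within 30 days of starting recovery, so 90 − 30 leaves about 60 earlier days. It could be fewer, because the inclusion criterion counts from referral and from detoxification or last use. If only a 7-day baseline window exists, adjust for the stratum alone.

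Keep the 6-month models on the stratum alone, or make baseline adjustment there optional and pre-specified. As the plan now reuses the primary model at 6 months, this has to be stated.

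Cost: SAP wording, one degree of freedom per model, possibly a longer baseline interview, a short script if SPSS 21 lacks HC3, and up to 1 to 2 power points if baseline drinking is not prognostic.

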Sample size: We plan to screen approximately 150 Veterans and recruit 110 Veterans (after telephone screen) with a current and primary DSM-V AUD who are within the first 30 days of recovery and expect that 90 will be eligible for randomization after baseline testing. We expect better than a 90% retention rate at the 3 month time point, and thus expect to have more than 80 individuals for the primary analysis. Assuming equal loss-to-follow-up in each of the two treatment arms, we will have at least 40 individuals per group. Using data

from our pilot study and the study done by Bowen et al., we estimate mean Days of Alcohol Use in the Placebo + IDC arm to be 4 and the number of Heavy Drinking Days to be 3 at 90 days. Using PASS 12 (Kaysville, Utah) Poisson regression procedure, and assuming an over-dispersion parameter of 2 for days of use and 4 for heavy drinking days, we will be able to detect a 37% reduction in days of use and a 55% reduction in days of heavy drinking with 80% power and a type I error rate of 5% for each outcome in the CRT+IDC arm compared to the Game-Play Placebo + IDC arm. Stratification on neurocognitive functioning was not factored into the sample size calculations. In most situations, stratification will increase precision, and thus we will have a conservative estimate of the detectable effects. Given that we expect to lose another 5-10% of individuals to follow-up, we will have less power to detect the same effect size at 6 month time point.

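### The 80% power for 37% and 55% reductions comes from a formula with a smaller variance than the planned over-dispersed Poisson test, which has about 73% and 68–72% on a two-sided reading

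*Combined protocol and SAP*

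**What the plan says.** All references are to the section on data management, sample size calculation and analysis plan of the combined protocol and SAP.

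- **Control means.** For days of use, "we estimate mean Days of Alcohol Use in the Placebo + IDC arm to be 4". For heavy drinking days, the plan takes "the number of Heavy Drinking Days to be 3 at 90 days".
- **Method.** The figures are obtained "Using PASS 12 (Kaysville, Utah) Poisson regression procedure", "assuming an over-dispersion parameter of 2 for days of use and 4 for heavy drinking days".
- **Result.** The plan says it can "detect a 37% reduction in days of use and a 55% reduction in days of heavy drinking with 80% power", with "a type I error rate of 5% for each outcome". It does not say whether the 5% is one- or two-sided.
- **Numbers analysed.** Ninety are randomised 1:1. Retention above 90% at 3 months is expected to leave more than 80 for the primary analysis, and at least 40 per group.
- **Stratification.** It was left out of the calculation, and the plan therefore calls its detectable effects conservative.
- **Planned test.** The Analysis Plan says "We will use a Poisson regression model accounting for over-dispersion", adjusted (as in all models) for the stratification variable. It does not name the test statistic (Wald, score or likelihood ratio). A negative binomial model is the sensitivity analysis.

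**The concern.** A sample-size formula is useful only if its variance is the variance of the test that will be run. In a Poisson model the standard error of the log rate ratio depends on the event counts in both arms. When treatment lowers the rate, the treated arm contributes fewer events and the standard error rises. A formula that sets the null variance as if both arms had the control rate leaves this out of the significance threshold, so it overstates power when the effect is a reduction. The larger the reduction, the larger the overstatement.

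These detectable effects are the plan's only statement of power for the primary outcomes. If they are optimistic, a null result would be read against a sensitivity the trial does not have, and the planning of the larger confirmatory study that the Analysis Plan mentions would inherit the error.

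**Working it through.** **Inputs.** From the sample-size paragraph: n = 40 per arm (N = 80); control mean μ0 = 4 (days of use) and 3 (heavy drinking days); rate ratio RR = 1 − 0.37 = 0.63 and 1 − 0.55 = 0.45; over-dispersion φ = 2 and 4; α = 5% per outcome. Assumed: two-sided test (z = 1.960), φ the same in both arms, no stratum term.

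**Step 1. Reproduce the plan's figures.** The formula assumed to lie behind the named procedure is

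power = Φ{ [ |ln RR| · √(N μ0/φ) − 1.960 · √V0 ] / √V1 }, with V0 = 4 (both arms at the control rate) and V1 = 2 + 2/RR.

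- Days of use: |ln 0.63| = 0.4620; √(80 × 4/2) = 12.649; V1 = 5.175. (5.844 − 3.920)/2.275 = 0.846, so power is 80.1%.
- Heavy drinking days: |ln 0.45| = 0.7985; √(80 × 3/4) = 7.746; V1 = 6.444. (6.185 − 3.920)/2.539 = 0.892, so power is 81.4%.

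Solved for 80% power, the formula gives reductions of 36.9% and 54.2%. The plan's 37% and 55% reproduce.

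**Step 2. The variance of the planned test.** SE(ln RR) = √{ φ · [1/(n μ0) + 1/(n μ1)] }, with μ1 = μ0 · RR.

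- Days of use: √{2 × (1/160 + 1/100.8)} = 0.180. The null SE in Step 1 is √{2 × (2/160)} = 0.158. 0.4620/0.180 = 2.57, and Φ(2.57 − 1.96) = 72.9%.
- Heavy drinking days: √{4 × (1/120 + 1/54)} = 0.328, against √{4 × (2/120)} = 0.258. 0.7985/0.328 = 2.44, and Φ(2.44 − 1.96) = 68.3%.

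**Step 3. Other test statistics, and simulation.** The table shows power at the stated reductions. Simulations used 60,000 trials per setting, with φ estimated by Pearson chi-square.

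| Two-sided 5%, no stratum term | Days of use, 37% | Heavy drinking days, 55% |
|---|---|---|
| Wald formula, 40 per arm | 72.9% | 68.3% |
| Score formula, 40 per arm | 73.6% | 70.6% |
| Simulated Wald (t or normal cutoff), variance = φ × mean, 40 per arm | 72.7–73.8% | 70.6–71.7% |
| Simulated likelihood ratio, same data | 73.2–74.2% | 72.3–73.2% |
| Wald formula, 45 per arm | 77.8% | 73.4% |
| Simulated Wald, variance = φ × mean, 45 per arm | 78.1–78.9% | 75.9–76.8% |
| Simulated Wald, common negative binomial shape, 40 per arm | 77.4–78.4% | 80.4–81.3% |
| Simulated Wald, common negative binomial shape, 45 per arm | 81.9–82.6% | 85.5–86.2% |

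In the negative binomial rows φ holds in the control arm only; the treated arm's variance-to-mean ratio falls with its mean.

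**Step 4. What 80% power corresponds to at 40 per arm.** Under constant φ, the detectable reductions are 40.0% (Wald) or 39.7% (score) for days of use, and 62.4% (Wald) or 60.4% (score) for heavy drinking days.

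**Step 5. The stratum term.** The documents give no stratum effect, so this is illustration only. Assume two equal strata with rate ratio R, and read φ as the overall control-arm dispersion. The within-stratum value is then φw = φ − μ0 · [(R − 1)/(R + 1)]², and the Step 2 SE is multiplied by √(φw/φ).

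- R = 1.5: φw = 2 − 4 × 0.04 = 1.84 and 4 − 3 × 0.04 = 3.88. Wald power is 76.4% and 69.6%.
- R = 2: φw = 2 − 4/9 = 1.556 and 4 − 3/9 = 3.667. Wald power is 83.0% and 72.1%.

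If φ is instead the residual dispersion after adjustment, this gain is nil.

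**The case against.** **The plan followed its named procedure correctly.** This stands. A reader might infer that the software was misused or the arithmetic is wrong. Step 1 shows otherwise: the figures follow from the plan's inputs. The disagreement is over which null variance applies.

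**The test may be one-sided.** The documents do not say, and the hypothesis for the primary aim is directional. A one-sided 5% Wald test at 40 per arm has 82.2% and 78.6% power, and its detectable reductions at 80% are 35.9% and 56.0%, each about one point from the plan's. The two-sided formula fits slightly closer (36.9% and 54.2%), so two-sided is the likelier reading, but it remains an assumption.

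**The calculation omits the planned stratum adjustment.** This stands in part. Step 5 shows that a stratum rate ratio near 2 would bring days of use above 80%, while heavy drinking days would stay short. No stratum effect is stated, so neither the gain nor the claim that the effects are conservative can be sized.

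**The shortfall depends on the variance model and on attrition.** This also stands. A reader might infer that both outcomes fall below 80% whatever is assumed. They do not: with a common negative binomial shape, heavy drinking days reaches 80–81% at 40 per arm, and both outcomes pass 80% with 45. But a single over-dispersion parameter per outcome in a Poisson model, which is what the plan states, implies constant φ. On that basis both outcomes remain below 80% even with no attrition.

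**The plan already concedes limited sensitivity.** It expects significance only with large effects and calls for a larger confirmatory study. That lowers the stakes but does not make the 80% correct for the planned test.

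**Conclusion.** The concern holds as a mismatch between the sample-size formula and the planned test. Assuming a two-sided 5% level, 40 per arm, constant over-dispersion of 2 and 4 in both arms and no stratum term, power at the stated reductions is about 73% for days of use and 68–72% for heavy drinking days, against the stated 80%. On the Wald formula the type II risk is about 27% and 32% rather than 20%. With all 90 analysed, power is about 78% and 73–77%.

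A reader might go further and take the pilot's 87.3 abstinent days out of 90, that is 2.7 days of use, as the placebo rate, which would lower power again. The documents do not support this. That figure is the cognitive-training arm of a pilot that mixed alcohol with other substance use disorders, and the comparator's mean is not given. Nor does the finding show that N = 90 must rise; it shows that the sensitivity claimed for 90 should be restated.

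**What to change.** Keep N = 90 and rewrite the sample-size paragraph.

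1. State that the 5% level is two-sided, if that is the intention, and name the test statistic.
2. Replace the 80% statement with figures from the variance of the planned test, φ × [1/(n μ0) + 1/(n μ1)], or from simulation of the stratum-adjusted model under a stated stratum effect. Without a stratum effect, the text would say that 40 per arm gives about 73% power for a 37% reduction in days of use and about 70% for a 55% reduction in heavy drinking days. Equivalently, 80% power corresponds to reductions of about 40% and 60–62%.
3. Say which variance model is assumed (constant φ or a common negative binomial shape), since the heavy drinking days figure moves by about 10 points between them.
4. Remove the statement that the detectable effects are conservative, unless a simulation with a stated stratum effect supports it. Do not add a figure based on the pilot's 2.7 days.

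The cost is one reworded paragraph and, at most, a short simulation. The stated sensitivity becomes slightly less favourable. No extra participants are needed, and the design and analysis do not change.
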